#### 3.3.4.6. Embryo Transfer

Anesthesia was not necessary for the embryo transfer procedure (Orvieto et al., 2009). Based on the patient's age, clinical history, number of prior tries, and embryonic quality, the number of embryos selected for transfer was determined (Kamath et al.,2020). Using a flexible catheter (Gynetics®, Belgium) that goes through the cervix and the vagina to enter the uterine cavity, fresh embryo transfer was performed. The patient was positioned in the lithotomy posture with a partially full bladder. To improve the outcome, the cervical mucus was removed and the vagina was gently cleaned with normal saline while being guided by transabdominal ultrasound. The highest morphological standards were used in the selection of the transferred embryos. The embryologist loaded and deposited the embryo into the uterus. The embryo was then examined under a microscope to ensure that every embryo had been transplanted. Typically, the embryo transfer process takes a few minutes. About 14 days following the embryo transfer, a pregnancy test was conducted to ensure the pregnancy was successful.

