# **Chapter Three Patients, Materials and Methods**

A prospective comparative study was conducted in the High Institute for Infertility Diagnosis and Assisted Reproductive Technologies, Al-Nahrain University in Baghdad, from January 2023 to January 2024. Ninety Iraqi women were included in this study. Every patient gave her written informed consent before taking part in the study figure (3-1), which was approved by the Ethical Committee of High Institute for Infertility Diagnosis and Assisted reproductive Technologies, Al-Nahrain University. They were evaluated twice during the study period and they did not receive any monetary compensation for their participation.

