# 3.1.1. Patient classification

- Group A: patients who receive (700IU) of intrauterine hCG
- Group B: patients who receive (500IU) of intrauterine hCG
- Group C: Control group patients did not receive any treatment.

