## **3.3.4.5.** Evaluation of fertilization and embryo grading :

Figure 3.6 illustrates the assessment of injected oocytes, which was carried out 16–18 hours after the ICSI to approve fertilization (Zygotes) and ensure the presence of two polar bodies and two pronuclei. If the fertilized oocytes had either 1PN or 3PN, they were deemed abnormal. It was considered that oocytes lacking PN were not fertilized. The following formula was utilized to calculate the fertilization rate: The calculation of fertilization rate is (total number of injected MII retrieved oocytes / number of fertilized oocytes (2PN) times 100 (Magaton et al., 2023).

Figure 3.6. Fertilized oocyte (appearance of two pronuclei) is an indicator of fertilization (Merchant et al. 2011)

First-day cleavage was assessed 24 hours after fertilization, and the number and size of blastomeres in each embryo were counted. On days 2 and 3 (48 and 72 hours after oocyte harvest), the amount, size, symmetry, and percentage of blastomere fragmentation determine how the embryos are graded. As seen in Figures 3.7–3.9, the developing embryos were morphologically graded according to the Istanbul consensus workshop prior to embryo transfer, where the embryo was classified into grades I, II, and III (Balaban et al., 2011).

Figure (3-7): Stages of human pre-implantation embryo development. Phase-contrast images of human embryo development from day (d) 0 to day 3. Following fertilization, embryos undergo a series of mitotic cell divisions. A: Zygote, B: 4 cells Grade 1, C: 8cells Grade 1(High Institute for Infertility Diagnosis and Assisted Reproductive Technologies, Al-Nahrain University, Iraq, Baghdad, 2023).

Grade II: High quality, most cells have stage-specific cell sizes, even in cell division embryos with 10–25% fragmentation.

Figure 3.8: Adapted from the High Institute for Infertility diagnosis and Assisted Reproductive Technologies, Al Nahrain University, Baghdad, Iraq; Day 3 grade 2 embryo 8 cells, equal size, 20% fragmentation

Grade III: Embryos of fair quality that show signs of multinucleation, fragmentation (>25%), and uneven cell division.

**Figure 3.9:** Adapted from the High Institute for Infertility diagnosis and Assisted Reproductive Technologies, Al Nahrain University, Baghdad, Iraq, Day 3 grade 3 embryos (5–6) cells, uneven, >25% fragmentation.

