## **3.3.8.** Pregnancy Test (P.T)

Pregnancy is documented by an elevated serum  $\beta$ -hCG level of  $\geq 6.5$  mIU/l in the 14th day following embryo transfer, and Progesterone treatment was continued up to 12 gestational weeks (Vaisbuch et al., 2012). Ultrasound examination is performed 6th week after E.T in order to confirm clinical pregnancy, viability and for diagnosis of multiplicity.

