## **3.3.9. HCG-Intrauterine Infusion**

HCG-intrauterine infusion done for 60 women undergoing ICSI to improve endometrial receptivity. Two different doses of hcg (diclair R)1500 IU were used for each patient. Drug was used on day of ova pick up. In the study group, the patient was put in the lithotomy position, and the cervix was visualized using Cusco's speculum. The cervical mucous was wiped out using a sterile piece of gauze, then the mucous was partially removed by gentle suction with a 1-mL syringe. A dummy ET was performed using a soft catheter (Wallace-Smiths Medical International Ltd.); if the soft catheter did not easily pass the internal cervical os, another more rigid but malleable catheter (Cook IVF) was used. After the catheter had passed the internal cervical os.

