# 3.3.9.1. Preparation of hCG

HCG dose was prepared by using , 1 ml of tissue culture media (G.2 plus ref. 10132, Vitrolife) to one vial containing 1500 IU of hCG (Diclair®). The injection dissolved immediately after completion of ova pick up and infused directly to endometrial cavity. 35  $\mu$ L of tissue culture mediam containing 500, or 47  $\mu$ L of tissue culture media containing 700 IU of hCG was injected intrauterine. Dose prepared by using (1 ml) of gain medium to dissolve hcg injection and dose for each patient loaded by using IUI (Gyntics) catheter.

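### The number of embryos transferred is decided woman by woman after hCG is given, but pregnancy is compared per woman with no account of that number or of what drives it

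*Protocol*

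**What the plan says.** **Choice of number.** Protocol section 3.3.4.6 (Embryo Transfer) lets the number vary by woman. It depends on her age, "clinical history, number of prior tries, and embryonic quality, the number of embryos selected for transfer was determined". No fixed number or range is stated.

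**Timing.** Section 3.3.9 says of the hCG: "Drug was used on day of ova pick up". Section 3.3.9.1 agrees: "The injection dissolved immediately after completion of ova pick up and infused directly to endometrial cavity". Embryos are graded later, "On days 2 and 3 (48 and 72 hours after oocyte harvest" (section 3.3.4.5), and quality is one of the inputs to the number chosen.

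**Design.** Chapter Three says "A prospective comparative study was conducted", without describing how women were allocated. Section 3.1.1 reads "Group C: Control group patients did not receive any treatment". Neither document mentions a sham infusion or masking.

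**Outcome.** Section 3.3.1 records the biochemical pregnancy rate from serum beta-hCG on day 14 after transfer. Section 3.3.8 adds an ultrasound in the 6th week to "confirm clinical pregnancy, viability and for diagnosis of multiplicity". Neither section forms an implantation rate per embryo.

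**Analysis.** The SAP lists t-tests, ANOVA, a paired t-test, chi-square and Fisher's exact test. Pregnancy, as a yes/no variable, falls under the last two. Nothing in the SAP uses the number of embryos, age or any other covariate.

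**The concern.** The chance that a woman becomes pregnant rises with the number of embryos placed, even if her endometrium is no more receptive. The number is settled after treatment, by a decision that the documents do not describe as shielded from group. It also depends on age and previous attempts, which may bear on pregnancy themselves, and no randomisation is described that would balance them.

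If the groups differ in number, or in those drivers, the unadjusted comparison attributes the consequence to hCG. The error can run either way: more embryos in an hCG group could mimic a benefit, and fewer could mask one. Section 3.3.9 gives the purpose of the infusion: "HCG-intrauterine infusion done for 60 women undergoing ICSI to improve endometrial receptivity". A reader will take a difference in pregnancy rate as evidence on that purpose, so the plan should show whether embryo number could explain it.

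**Working it through.** The documents give no pregnancy rate, embryo count, effect size or sample-size basis, so there is no planned figure to reproduce. What follows is an illustration.

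**Inputs from the documents.** Total 90 women (Chapter Three); 60 receive hCG (section 3.3.9); controls by subtraction 90 − 60 = 30; significance level 0.05 (SAP).

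**Assumed inputs.** Implantation probability per embryo p from 0.10 to 0.25, equal in all groups and independent between embryos; 2 or 3 embryos per woman; the 60 treated women split 30/30 between doses.

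**Formula.** Pregnancy per woman with k embryos = 1 − (1 − p)^k. Moving from 2 to 3 embryos adds p(1 − p)².

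| p | 2 embryos | 3 embryos | Gap |
|---|---|---|---|
| 0.10 | 1 − 0.90² = 19.0% | 1 − 0.90³ = 27.1% | 8.1 points |
| 0.15 | 27.8% | 38.6% | 10.8 points |
| 0.20 | 36.0% | 48.8% | 12.8 points |
| 0.25 | 1 − 0.75² = 43.8% | 1 − 0.75³ = 57.8% | 14.1 points |

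These gaps are the extreme case in which every woman in one group receives 3 and every woman in the other receives 2.

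**Smaller imbalance.** If the share of women receiving a third embryo differs by 30 or 40 percentage points, the mean number differs by 0.3 or 0.4 and the gap scales in proportion:
- p = 0.10: 0.30 × 8.1 = 2.4 points; 0.40 × 8.1 = 3.2 points.
- p = 0.25: 0.30 × 14.1 = 4.2 points; 0.40 × 14.1 = 5.6 points.

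**Chance of a false positive.** This is the probability of p < 0.05 in the favoured direction with no hCG effect, against a nominal 2.5%.

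| Imbalance | 30 v 30 | 60 v 30 (both doses pooled) |
|---|---|---|
| 3 v 2 for every woman | 11% to 19% | 12% to 24% |
| Mean difference 0.3 to 0.4 | 4% to 6% | 4% to 7% |

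**Can prognosis reverse the picture?** Section 3.3.4.6 ties the number to prognostic factors, so p need not be the same for women given 2 and women given 3. Suppose p = 0.25 with 2 embryos and p = 0.175 with 3. Pregnancy per woman is then 1 − 0.75² = 0.4375 and 1 − 0.825³ = 0.4385. The gap vanishes, while the per-embryo rates are 25% and 17.5%. An implantation rate taken alone would then suggest a receptivity difference that prognosis had produced.

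**The case against.** The strongest reply has five parts.

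- **Receptivity is not judged on pregnancy alone.** The title names receptivity and ICSI outcome as separate aims. Doppler and cytokines are measured at pick-up and again on transfer day, and endometrial thickness is measured as well. The number of embryos placed cannot alter measurements taken by the time of transfer. This stands. A reader might infer that the whole receptivity assessment fails, but the documents do not support that.
- **Knowledge of group is inferred.** The untreated control and the absence of any described masking make it plausible that the deciding team knew the group. The documents give only the order of events, and group is not among the listed criteria. This stands.
- **If the listed criteria are followed, a difference in number is mostly ordinary confounding by prognosis.** This is largely right, since hCG placed in the uterus is not expected to act on embryos in culture. But the unadjusted analysis deals with neither route.
- **The 14-point gap is extreme.** This stands. At 30 v 30 and a rate of 43.75%, the standard error of a difference is √(2 × 0.4375 × 0.5625 / 30) = 0.128, about 13 points. A shift of 2 to 6 points is small beside it.
- **The per-embryo rate can itself mislead.** This stands, as the 25% against 17.5% example shows, and it shapes the fix.

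The requirement for grade 1 embryos in section 3.1.2 restricts quality, not number, so it does not answer the point.

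**Conclusion.** The point holds as an uncontrolled risk to the pregnancy comparison. Number transferred is individualised and settled after hCG, with no described randomisation, sham or masking, and the SAP's only tests for pregnancy ignore it.

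Two further readings go beyond the documents. One is that the groups did receive different numbers: no counts by group are given, so neither the size nor the direction of any bias is known. The other is that implantation per embryo would settle receptivity: under selection by prognosis it is also open to confounding.

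Under equal, independent implantation of 10% to 25% per embryo, the spurious difference is 8 to 14 points in the extreme case and about 2 to 6 points for a mean difference of 0.3 to 0.4 embryo. If women given more embryos have a lower chance per embryo, the gap shrinks and may vanish.

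**What to change.** Change the analysis and reporting only; nothing here prescribes how many embryos to transfer.

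1. Tabulate the number of embryos transferred by group, with day and grade.
2. Keep the unadjusted test. Add a per-woman pregnancy comparison adjusted for number transferred and age, and for previous attempts if they were recorded. Logistic regression would serve, or an exact or penalised version if events are few. Age is needed as well because number alone leaves confounding by prognosis.
3. Label this a sensitivity analysis, and post hoc if the data have been seen. That seems likely, as the study ran to January 2024 and the SAP text sits in a results chapter dated October 2024.
4. Where sac counts were recorded at the 6th-week scan, report sacs divided by embryos transferred, with standard errors clustered by woman. Define the numerator, since sacs lost before the scan may be missed. Present the rate as supportive and not as the sole receptivity measure, and state that confounding by prognosis remains.

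**Cost.** SAP wording, one table and one or two models. The questionnaire has an embryo-transfer line that appears to hold number, day and grade, though its text is damaged. No sac-count field is legible, so step 4 depends on what was recorded. One to three extra parameters with about 30 women per group (equal dose split assumed) will widen intervals somewhat. Adjustment reduces the problem but cannot replace a decision made without knowledge of group.

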#### **3.3.4.7.** Luteal Phase Support

The luteal phase was maintained starting from oocyte retrieval day through the administration of vaginal progesterone (Cyclogest®400mg twice daily; Actavis, UK®) and progesterone injection (depote 250-500 mg twice weekly) for a duration of 14 days. This regimen continued until the  $\beta$ -HCG test was conducted; in case of a positive result, progesterone intake was sustained until 9-12 weeks, coinciding with the initiation of placental activity (Zhang et al. 2020).

#### **3.3.5. Samples collection**

### 3.3.5.1. Blood Sampling

Blood Sampling for TNF- $\alpha$  & IL-10, on the day of OPU and day of embryo transfer for both hCG group together with control group and according to the number and grading of the embryos, patients were prepared for the transfer. The patient's serum was obtained by aspirating the blood samples from the median cubital vein by disposable syringe (Becton Dickinson company, USA), into a serum separating tube (gel & clot activator, AFCO, Jordan), and allowed to clot for 30 minutes. Serum was obtained after centrifugation at a rate of 5000 rpm for 5 minutes. All samples were kept in a sterile container labeled with patient's study number. Samples were refrigerated at -20°C until the time of examination using diagnostic Kit by (ELIZA) technique (IL-10, TNF, ELIZA Kit, Bio Source, USA).

### **3.3.6.** Biochemical Assay

### 3.3.6.1. Principle of the ELISA:

Enzyme-linked immunosorbent assay (ELISA) is a biochemical assay that uses antibodies and an enzyme-mediated color change to detect the presence of either antigen such as proteins, peptides, and hormones or antibody in a given sample (Gan SD.et al., 2013), Figure (3-10)

Figure (3-10): Enzyme-linked Immunosorbent Assay (ELISA) (Shan et al., 2002

#### **3.3.6.2. TEST PRINCIPLE FOR IL-10**

This kit uses enzyme-linked immune sorbent assay (ELISA) based on the Biotin double antibody sandwich technology to assay the Human Interleukin 10 (IL-10). Add Interleukin10 (IL-10) to the wells, which are pre-coated with Interleukin 10(IL-10) monoclonal antibody and then incubate. After that, add anti IL-10 antibodies labeled with biotin to unite with streptavidin-HRP, which forms immune complex. Remove unbound enzymes after incubation and washing. Add substrate A and B. Then the solution will turn blue and change into yellow with the effect of acid. The shades of solution and the concentration of Human Interleukin 10 (IL-10) are positively correlated figure (3-11).

Figure (3-11): ELIZA washer and shaker

#### **3.3.6.3. TEST PRINCIPLE FOR TNF-**α

This kit uses enzyme-linked immune sorbent assay (ELISA) based on the Biotin double antibody sandwich technology to assay the Human Tumor necrosis factor-alpha (TNF-alpha). Add Tumor necrosis factor-alpha (TNF-alpha) to the wells, which are pre-coated with Tumor necrosis factor-alpha (TNF-alpha) monoclonal antibody and then incubate. After that, add anti TNF-alpha antibodies labeled with biotin to unite with streptavidin-HRP, which forms immune complex. Remove unbound enzymes after incubation and washing. Add substrate A and B. Then the solution will turn blue and change into yellow with the effect of acid. The shades of solution and the concentration of Human Tumor necrosis factor-alpha (TNF-alpha) are positively correlated.

#### 3.3.6.4. Assay procedure for TNF-alpha:

• 100  $\mu$ L standard or sample to each well will be added. Incubate for 90 min at 37°C.

• The liquid will be removed. 100  $\mu$ L will be added Biotinylated Detection Ab. Incubate for 1 hour at 37°C.

• Aspiration and wash 3 times.

• 100  $\mu$ L HRP Conjugate working solution will be added. Incubate for 30 min at 37°C.

- Aspiration and wash 5 times.
- 90 µL Substrate Reagent will be added. Incubate for 15 min at 37°C.
- 50 µL Stop Solution will be added. Read at 450 nm immediately.
- Results will be Calculated.

## **3.3.7.** Ultrasonography Assessment:

## 3.3.7.1. Endometrial Thickness Measurement

The transvaginal scan was performed using the 5-9 MHz vaginal probe of SonoAceX6 Ultrasound Set, wall filters (50 Hz) were used to eliminate low frequency signals, Ultrasound machine was performed after placing patients with an empty bladder in the dorsal lithotomy position, a sweep through the mid-sagittal plane of the uterus was obtained to give a multiplanar display figure (3-12).

Figure 3.12: Versana Balance (ge-medical system) ultrasound equipment, CHINA, JIANGSU CHINA (High Institute for Infertility Diagnosis and Assisted Reproductive Technologies, Al-Nahrain University, Iraq, Baghdad, 2022).

Endometrial thickness of the uterus was measured, as the maximum distance from one basal endometrial interface across the endometrial canal to the opposite endometrial– myometrial interface, after the patient had completely emptied her bladder. The measurement involved both endometrial layers excluding the surrounding low amplitude echo layer, three measurements were taken & the average value was recorded figure (3-10).

Figure 3.13: Ultrasound review reveals myometrial, endometrial and subendometrial zones (Zhao et al., 2012)

#### 3.3.7.2. Two-Dimensional color doppler Ultrasound

After completion of the B-mode examination, a pulsed Doppler system was used for blood flow analysis. Sub endometrial vessels were visualized at the endometrial periphery, sometimes penetrating the hyperechogenic endometrial edge or even reaching the endometrial cavity (Elnaggar et al., 2017), The blood flow velocity waveforms from the subendometrial vessels were obtained by placing the Doppler gate over the colored area at zone 2 and activating the pulsed Doppler function. Figure (3-14)

Figure 3.14: A: Subendometrial blood vessels Doppler ultrasound velocimetry in a case of good receptive endometrium. B: Doppler blood flow till Zone 3

A recording was considered satisfactory when at least 3 consecutive uniform waveforms were obtained; each demonstrated the maximum Doppler shift. Three measurements for each parameter were taken and the average value was

recorded, Figure (3-12). Resistance index (RI) and pulsatility index (PI) were calculated automatically by ultrasound for both subendometrial vessels, according to the following formula figure (3-15):

Figure 3.15: three consecutive uniform waveform obtained from doppler study of patient attend high institute of infertility diagnosis and assisted reproductive technology.

$$\mathbf{RI} = \frac{\mathbf{PSV} - \mathbf{EDV}}{\mathbf{PSV}}$$
  $\mathbf{PI} = \frac{\mathbf{PSV} - \mathbf{EDV}}{\mathbf{mv}}$   $\mathbf{mv} = \frac{\mathbf{PSV} + \mathbf{EDV}}{2}$ 

RI: resistance index, PSV: peak systolic velocity, EDV: end-diastolic velocity, PI: pulsatility index, mv: mean velocity

Figure 3.16: Method of measurement of S/D, RI& PI

## **3.3.8.** Pregnancy Test (P.T)

Pregnancy is documented by an elevated serum  $\beta$ -hCG level of  $\geq 6.5$  mIU/l in the 14th day following embryo transfer, and Progesterone treatment was continued up to 12 gestational weeks (Vaisbuch et al., 2012). Ultrasound examination is performed 6th week after E.T in order to confirm clinical pregnancy, viability and for diagnosis of multiplicity.

## **3.3.9. HCG-Intrauterine Infusion**

HCG-intrauterine infusion done for 60 women undergoing ICSI to improve endometrial receptivity. Two different doses of hcg (diclair R)1500 IU were used for each patient. Drug was used on day of ova pick up. In the study group, the patient was put in the lithotomy position, and the cervix was visualized using Cusco's speculum. The cervical mucous was wiped out using a sterile piece of gauze, then the mucous was partially removed by gentle suction with a 1-mL syringe. A dummy ET was performed using a soft catheter (Wallace-Smiths Medical International Ltd.); if the soft catheter did not easily pass the internal cervical os, another more rigid but malleable catheter (Cook IVF) was used. After the catheter had passed the internal cervical os.

# 3.3.9.1. Preparation of hCG

HCG dose was prepared by using , 1 ml of tissue culture media (G.2 plus ref. 10132, Vitrolife) to one vial containing 1500 IU of hCG (Diclair®). The injection dissolved immediately after completion of ova pick up and infused directly to endometrial cavity. 35  $\mu$ L of tissue culture mediam containing 500, or 47  $\mu$ L of tissue culture media containing 700 IU of hCG was injected intrauterine. Dose prepared by using (1 ml) of gain medium to dissolve hcg injection and dose for each patient loaded by using IUI (Gyntics) catheter.

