Ministry of Higher Education and Scientific Research Al-Nahrain University High Institute for Infertility Diagnosis and Assisted Reproductive Technologies

Study the Effects of Intrauterine flushing with Low Dose Human Chorionic Gonadotrophin on Endometrial Receptivity and ICSI Outcome

OCTOBER 16, 2024

CHAPTER FOUR RESULTS

Statistical analysis

The data analyzed using Statistical Package for Social Sciences (SPSS) version 26. The data presented as mean, standard deviation and ranges. Categorical data presented by frequencies and percentages. Independent t-test and Analysis of Variance (ANOVA) (two tailed) was used to compare the continuous variables accordingly. Paired t-test was used to compare the continuous variables on pickup day and on transfer day. Chi square test was used to assess the association between categorical variables, while fisher exact test was used instead when the expected frequency was less than 5. A level of P – value less than 0.05 was considered significant.

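### The hCG preparation as written delivers 52.5 and 70.5 IU, about a tenth of the 500 and 700 IU that define the two treated groups

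*Protocol*

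**What the plan says.** Protocol section 3.1.1 separates the treated groups by dose alone. Group A is "patients who receive (700IU) of intrauterine hCG" and Group B is "patients who receive (500IU) of intrauterine hCG"; Group C is untreated. Section 3.3.9 gives the number treated: "HCG-intrauterine infusion done for 60 women undergoing ICSI to improve endometrial receptivity". The opening of Chapter Three puts the whole study at ninety women.

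Section 3.3.9.1 describes the preparation. It adds "1 ml of tissue culture media (G.2 plus ref. 10132, Vitrolife) to one vial containing 1500 IU of hCG" and later gives the same diluent volume again: "Dose prepared by using (1 ml) of gain medium to dissolve hcg injection". The infused amounts are 35 µL "of tissue culture mediam containing 500, or 47" µL "of tissue culture media containing 700 IU of hCG was injected intrauterine". So 35 µL is said to carry 500 IU and 47 µL to carry 700 IU. Section 3.3.9 repeats the 1500 IU product strength.

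The study title, on the SAP, describes the treatment as "Intrauterine flushing with Low Dose Human Chorionic Gonadotrophin on Endometrial Receptivity and ICSI Outcome".

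**The concern.** Vial strength, diluent volume and infused volume together fix the dose, and section 3.3.9.1 states all three. The dose they imply is about a tenth of the one stated in the same section and used in section 3.1.1 to name the groups.

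Dose is the only thing that distinguishes Group A from Group B, and it applies to 60 of the 90 women. If only a printed volume is wrong, the labels are sound and the damage is confined to the methods text. If the text is literal, both labels are about ten times too high, and any conclusion about 500 or 700 IU would concern doses nobody received. In either case the method cannot be repeated as written: someone following section 3.3.9.1 would give about 50 to 70 IU believing it to be 500 to 700 IU.

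**Working it through.** **Inputs**

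| Quantity | Value | Source |
|---|---|---|
| hCG per vial | 1500 IU | Protocol 3.3.9.1; strength repeated in 3.3.9 |
| Diluent | 1 ml = 1000 µL | Protocol 3.3.9.1, stated twice |
| Infused volumes | 35 µL and 47 µL | Protocol 3.3.9.1 |
| Stated doses | 500 IU (B) and 700 IU (A) | Protocol 3.1.1 and 3.3.9.1 |

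**Step 1: try to reproduce the stated doses.** Dose = infused volume × (IU per vial ÷ diluent volume).

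- Concentration: 1500 ÷ 1000 = 1.5 IU/µL.
- Group B: 35 × 1.5 = 52.5 IU, against 500 stated (500 ÷ 52.5 = 9.5).
- Group A: 47 × 1.5 = 70.5 IU, against 700 stated (700 ÷ 70.5 = 9.9).

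The stated doses are not reproduced.

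**Step 2: what would make them agree?**

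- Keeping 1 ml of diluent, the volumes needed are 500 ÷ 1.5 = 333 µL and 700 ÷ 1.5 = 467 µL.
- Keeping 35 and 47 µL, the diluent needed is 1500 × 35 ÷ 500 = 105 µL and 1500 × 47 ÷ 700 = 100.7 µL, so about 0.1 mL in both cases.

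**Step 3: the candidate readings.**

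| Reading | Concentration | Group B | Group A | A minus B |
|---|---|---|---|---|
| 1. Volumes misprinted tenfold (350 and 470 µL), 1 mL diluent | 1.5 IU/µL | 525 IU | 705 IU | 180 IU |
| 2. Volumes as printed, 0.1 mL diluent | 15 IU/µL | 525 IU | 705 IU | 180 IU |
| 3. Text literal | 1.5 IU/µL | 52.5 IU | 70.5 IU | 18 IU |
| As labelled | – | 500 IU | 700 IU | 200 IU |

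Under readings 1 and 2 the labels are close: 525 ÷ 500 = 1.050 and 705 ÷ 700 = 1.007.

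**Step 4: other ways to reconcile the text.**

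- Two vials in 1 ml give 3 IU/µL, hence 105 and 141 IU, which does not match.
- If the two mentions of 1 ml meant 2 ml in total, the concentration would be 0.75 IU/µL and the doses about 26 and 35 IU, which widens the gap.
- Ten vials in 1 ml would give 15 IU/µL and the same 525 and 705 IU as reading 2, but section 3.3.9.1 specifies one vial.
- No section gives a concentrating step or another infused volume.

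**The case against.** The best counter-argument accepts the arithmetic and says that a single decimal slip is by far the likeliest explanation. Both printed volumes point to nearly the same diluent (105 and 100.7 µL), as expected if someone worked at about 0.1 mL and aimed for 500 and 700 IU. Those doses are stated consistently in sections 3.1.1 and 3.3.9.1. There is also a stray comma just before the first mention of 1 ml, which could be the remains of a decimal point. On this view only a typographical correction is needed, no woman's dose was far from its label, and no test in the SAP changes.

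Much of this stands. A tenfold slip is plausible, and it would be wrong to assert that women were under-dosed. But the comma does not settle the matter, because the second mention of 1 ml in the same section has no such mark. The volumes could equally be the misprint. That the doses are stated consistently shows what was intended, not what was drawn up: a slip made when the volumes were calculated and then followed at the bench would leave the same text.

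It is also true that the comparisons of A, B and C as treated survive every reading, provided one preparation was used throughout, which the documents do not confirm. That limits the problem to the IU figures attached to the groups, but those figures are how the groups are defined. The words low dose in the title do not help choose between readings, since no threshold is given.

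**Conclusion.** The concern holds. Taking one vial and 1 ml as stated, the preparation in Protocol section 3.3.9.1 yields 52.5 and 70.5 IU, not 500 and 700 IU: a discrepancy of 9.5-fold for Group B and 9.9-fold for Group A. The diluent volume, the infused volumes and the group doses cannot all be right.

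The documents do not say which is wrong. If the slip is in the printed volumes or the diluent, the delivered doses were about 525 and 705 IU and the labels are right to within 5%. If the text is literal, the labels are about ten times too high and the A-versus-B contrast was 18 IU. The calculation needs no outside figure. Because dose defines two of the three groups, this has to be resolved before any conclusion is tied to a specific IU dose.

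**What to change.** 1. Establish the diluent volume and infused volumes actually used, from preparation records if they exist and otherwise from the operators' standard procedure. Confirm that one preparation was used throughout.
2. Correct section 3.3.9.1 so that concentration times volume equals the group dose. With 1 mL of diluent that means 333 µL for 500 IU and 467 µL for 700 IU. If 35 and 47 µL were infused, state a diluent of about 0.1 mL.
3. If the delivered amounts were not 500 and 700 IU, relabel Groups A and B with the delivered amounts in the analysis and conclusions.
4. Only if the amounts cannot be established, report the dose as uncertain (about 53 and 70 IU, or about 500 and 700 IU), describe the groups as lower-volume, higher-volume and untreated, and draw no conclusion about a specific IU dose.

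Two wording points can be settled at the same time, though the calculation does not depend on them. Section 3.3.9.1 names two diluents, G.2 plus and GAIN, while Table 3.2 lists only the latter. Section 3.3.9 reads as if each woman received both doses and should say that each received one.

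The cost is a check with the clinic and a text correction; no new patients are needed. Treatment ran from January 2023 to January 2024 and the protocol describes no preparation record, so the delivered dose may prove unrecoverable, though that silence does not show that records are missing. In that case the cost is giving up any claim about a specific IU dose.
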